Course of work productivity and work ability, the course of health-related quality of life, and changes in functionality under long term treatment with adalimumab will be documented. The numbers of patients included in the NIS allow identifying and quantifying the impact of disease and patient characteristics on the therapeutic success.

7 Study Objectives

In this NIS, a long term documentation of treatment with adalimumab in RA patients over 60 months with 8 data collection points (visits) is planned. The documentation will be performed by the physician as well as by patient's self-assessment.

The primary objective is to explore the therapeutic success by interim analyses after 12 and 24 months of treatment as well as by the final analysis after 60 months of treatment. Improvements concerning the following target variables will be evaluated (with regard to the respective baseline value):

- the number of missed working days
- the self-assessed work ability (WPAI)
- the severity of clinical symptoms (number of tender and swollen joints, CRP and ESR, respectively; total score DAS28)
- Severity of functional impairment (HAQ)
- The health-related quality of life (EQ-5D)

At month 3, patient and disease characteristics will be evaluated with regard to their additional impact on changes in the number of affected joints (DAS28), in the HAQ, and in the WPAI. The impact on the number of missed working days will be evaluated at month 6.

The secondary objective is to document the therapeutic success by interim analyses at month 12 and 24 months as well as by the final analysis after 60 months. The therapeutic success will be evaluated by the following variables:

- The number of physician visits
- The number and duration of hospitalizations
- The number of days of impairment in non-occupational activities
- The duration of morning stiffness, pain, exhaustion/fatigue

- The reduction of number and dose of concomitant medication
- Patient's assessment of adalimumab therapy compared to previous therapies

Target parameters for safety evaluation of adalimumab are:

- The evaluation of safety and tolerability by the documentation and analysis of serious adverse events (SAEs) and adverse events (AEs).
- Evaluation of safety and tolerability for subgroups of patients with common frequent concomitant diseases, especially diabetes type II, cardiovascular, liver, and renal insufficiencies, and related concomitant medications.

8 Investigational Plan

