8.1 Selection of Study Population

This study population will consist of adult patients (≥ 18 years) with moderate to severe active rheumatoid arthritis (RA) who have failed other anti-rheumatic drugs including Methotrexat (MTX) and patients with a severe, active and progressive rheumatoid arthritis (with or without prior MTX).

Patients who have been previously treated with other biologics (including TNF inhibitors) can be included in the NIS.

The inclusion and exclusion criteria adhere to the approved label as stated in the German Summary of Product Characteristics (SPC) “Fachinformation” for HUMIRA®. No additional inclusion and exclusion criteria are applicable since this project is non-interventional.

Patients to be included will be informed about the NIS and the use of their anonymous data. Patients willing to participate must provide their written informed consent to the investigator before entry into the NIS. The signed informed consent form will be added to the patient's file.

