8.4 Study Duration

The duration of the whole NIS is estimated to be about 9 years.

Study start: March 2009

Recruiting phase: March 2009 – March 2012

Data completion: March 2017

Data analysis and final report: March 2017 – March 2018

For each individual patient, the NIS starts with the enrollment in the long term documentation at the beginning of the treatment with adalimumab and ends either after 5 years or with the termination of the adalimumab therapy.

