Laboratory values: Hepatitis B, Hepatitis C, tuberculosis screening, TB prophylaxis (if necessary) ⁶	X	X ⁷	X ⁷	X ⁷				
Adverse events		X	X	X	X	X	X	X
Patient's compliance		X	X	X	X	X	X	X

¹ Month 60 or last visit

² after baseline visit (month 0) only if current radiograph is available or if indicated

³ after baseline visit (month 0) only for newly developed diseases or changed therapy

⁴ after baseline visit only for changes in therapy or dose

⁵ Data are part of the DAS28 (Disease Activity Score)

⁶ after baseline visit (month 0) only if data is available or if indicated

⁷ only TB prophylaxis documented

Table 2. Patient Schedule

	Month							
	0	3	6	12	24	36	48	60
Personal data	X							
Education	X							
Professional status	X		X	X	X	X	X	X
Missed working days (last 6 months)	X		X	X	X	X	X	X
Physician visits and hospitalization (last 6 months)	X		X	X	X	X	X	X
Days of impairment in non-occupational activities	X		X		X	X	X	X
Work ability (WPAI)	X	X	X	X	X	X	X	X
Exhaustion/fatigue (last 7 days)	X	X	X	X	X	X	X	X
Pain (last 7 days)	X	X	X	X	X	X	X	X
Functionality (HAQ)	X	X	X	X	X	X	X	X
Health-related quality of life (EQ-5D)	X	X	X	X	X	X	X	X
Patient's assessment of adalimumab ther- apy compared to previous therapies		X	X	X	X	X	X	X
Participation Abbott Care service program	X	X	X	X	X	X	X	X

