12.3 Missing Values

Missing observations will be documented as missing values. Instructions for the minimum documentation required for a patient to be evaluable will be established in the SAP.

All data will be analyzed on the basis of “observed cases”. For the statistical analysis of data concerning the course of disease, the health-related economic parameters and

the health-related quality of life (if related to changes from baseline values), an additional approach will be followed considering only patients with complete data at all visits.

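### The rating of adalimumab against earlier therapies is listed as therapeutic success, but entry after earlier failure and the loss of patients who stop both tilt it towards adalimumab

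*Combined protocol and SAP*

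**What the plan says.** All references are to the Combined protocol and SAP unless stated otherwise.

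- **Role.** Section 7 introduces the secondary variables with "The therapeutic success will be evaluated by the following variables" and includes "Patient's assessment of adalimumab therapy compared to previous therapies", with interim analyses at Months 12 and 24 and a final analysis at Month 60. The synopsis (Section 2) has the same item.
- **Entry.** Section 8.1 gives two routes. One is moderate to severe active disease in patients "who have failed other anti-rheumatic drugs including Methotrexat (MTX"). The other is "severe, active and progressive rheumatoid arthritis (with or without prior MTX"). The split between the routes is not given. Earlier biologics are allowed.
- **End of follow-up.** Under Section 8.4 a patient's documentation "ends either after 5 years or with the termination of the adalimumab therapy".
- **Schedule.** The patient schedule (Table 2, Section 8.5.1) asks for the rating at Months 3, 6, 12, 24, 36, 48 and 60, with no Month 0 value. The note "Month 60 or last visit" belongs to the physician schedule (Table 1) and is not attached to Table 2.
- **Missing data.** Section 12.3 prescribes observed cases. It adds a complete-data analysis for several outcome groups and does not say whether this rating is among them.
- **Analysis.** Section 12.5 does not name the rating. No scale, neutral value, denominator or rule for patients without a previous therapy is given.
- **Discontinuation.** Section 1.9 of the Protocol (AGIL-CV amendment) expects about 50% to discontinue over 60 months.

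**The concern.** The study has a single arm (8.5.1), so nothing shows how patients would rate any new drug after a switch. This item is the patient's own look back at earlier treatment and has no baseline value, so adjustment for baseline cannot repair it.

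Two kinds of selection act on it. For patients who enter through the failure route, the therapy being compared has already performed poorly. After entry, ratings at a given visit come only from patients still documented, which under 8.4 means patients still on adalimumab. If those who stop are on average the poorer responders, the share rating adalimumab better rises over time without any change in the drug's effect.

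The stake is interpretation. A high percentage rating adalimumab better, reported under therapeutic success, could arise with a drug no better than its predecessors. With no denominator or reference value fixed, a reader of the results could not tell.

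**Working it through.** The documents give no figure for this rating, so there is none to reproduce. The check asks what share would rate adalimumab better if it were exactly as good as the earlier therapy.

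**Inputs**

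- From the documents: 50% discontinued by Month 60 (Protocol, AGIL-CV amendment, Section 1.9).
- Assumed: response to the earlier therapy (A) and to adalimumab (B) follow the same normal distribution, with within-patient correlation ρ of 0 or 0.5. A patient rates adalimumab better if B > A.
- Assumed: failure means A lies in the lowest 30%, 50% or 70%. The share m entering by failure is 50%, 75% or 100%, and the others are unselected.
- Assumed: patients with low B stop, with a full or a weak link (correlation 0.5) between response and stopping.

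**Step 1: no selection.** By symmetry P(B > A) = 50%.

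**Step 2: entry selection alone.** For ρ = 0 and failure in the lowest fraction f, P(B > A | failure) = 1 − f/2. This gives 85%, 75% and 65% for f = 0.3, 0.5 and 0.7. At ρ = 0.5, simulation with 2 million patients gives 74%, 67% and 60%. With a share m entering by failure, the overall share is m × P(B > A | failure) + (1 − m) × 50%.

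- Lowest value (f = 0.7, ρ = 0.5, m = 0.5): 0.5 × 60.2% + 0.5 × 50% = 55%.
- Highest value (f = 0.3, ρ = 0, m = 1): 85%.
- With only half entering by failure, the range is 55% to 68%.

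**Step 3: stopping alone, half lost.** If the half with the lower value of a stopping variable is lost, P(B > A | retained) = 1/2 + arcsin(r)/π, where r is the correlation of that variable with B − A. With a full link r = √((1 − ρ)/2); with the weak link r is half of that.

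| Link between response and stopping | ρ = 0 | ρ = 0.5 |
|---|---|---|
| Full | r = 0.707, 75% | r = 0.5, 67% |
| Weak (0.5) | r = 0.354, 62% | r = 0.25, 58% |

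The simulation gives the same rounded figures. If stopping were unrelated to response, this step would add nothing.

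**Step 4: both together, half lost.** With a full link the simulation gives 76% to almost 100% over the grid. With the weak link, and all entrants from the worse half on earlier therapy, it gives 86% (ρ = 0) and 79% (ρ = 0.5).

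Every scenario run lies above 50%.

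**The case against.** The strongest reply is that no superiority claim is planned. The study is exploratory with unadjusted p-values (12.4), Section 12.5 gives this rating no test or model, and the stated aim is to document. Whether patients feel better than on their previous therapy is a fair descriptive question in routine care. Section 12 also defers detail to a separate SAP. This stands as a limit on severity: one of six secondary variables is affected. It does not remove the point, because the label of therapeutic success stands in Sections 2 and 7 themselves.

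Several stronger readings are tempting and go beyond the documents:

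- *Most patients enter because earlier therapy failed, and those who did well never enter.* Section 8.1 gives no split, and the second route does not require failure.
- *Section 8.1 admits patients with no earlier therapy.* It says with or without prior MTX, and Section 8.5.2 records other earlier drugs. Untreated entrants are possible but not stated.
- *Patients who stop are not asked.* Many will have rated at earlier visits. Section 11 says the CRF has patient forms for each visit, so collection at a last visit is unclear rather than excluded.
- *Nobody would rate adalimumab worse, and 80% would rate it better at Month 60.* With a binary responder model and 40% response, conditioning on earlier failure leaves 40% better and 0% worse by construction. Dividing 40% by the 50% retained gives 80% only if every stopper is a non-responder. Patients could rate adalimumab worse for tolerability, or because an earlier drug helped in part.

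The attrition part also touches other outcomes analysed as observed cases. What is particular to this rating is the preselected comparator and the absence of a baseline value. The LOCF rule in the AGIL-CV amendment (Protocol, Section 1.10) belongs to that supplement and does not cover it.

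**Conclusion.** The point holds as a limit on interpretation. As planned, the rating is tilted towards adalimumab by entry selection and, increasingly at later visits, by loss of patients who stop. No other section corrects this. For equally good drugs the illustration moves the share rating adalimumab better from 50% to about 55-85% through entry selection alone. Loss of half the patients by Month 60 alone moves it to about 58-75%.

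The sizes depend on the assumed continuous responses, failure thresholds, share entering by failure and link between stopping and response. The direction needs only that some patients enter through failure, or that stoppers tend to be poorer responders; a majority entering by failure is not required. A reader might infer that the main efficacy conclusions are compromised. The documents do not support that, since the item is secondary and bears on neither the primary objective nor the sample size. The change is worth making because it is cheap.

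**What to change.** 1. In Sections 2 and 7, describe the item as a patient-reported preference or satisfaction rating rather than a measure of therapeutic success, and state that the comparator is often a failed therapy.
2. Report it at Month 3 and at Months 12, 24 and 60. The denominator should be all patients who started adalimumab and had a previous therapy.
3. Show separate categories: better, same, worse, stopped adalimumab (with the last rating given before stopping), and missing. Do not count stoppers as not rated better. That would override favourable ratings already given, treat stopping for any reason as an unfavourable rating and, with 50% stopped, cap the Month 60 share at 50%.
4. Show patients without a previous therapy as not applicable, and split the table by previous biologic yes or no.

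Previous therapies, including biologics, are already recorded at baseline (Section 8.5.2), so no new data are needed. The three rating categories assume that the form's answers can be grouped this way, since the documents do not give the scale. The cost is the rewording, one added table and a less favourable headline percentage.

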8.1 Selection of Study Population

This study population will consist of adult patients (≥ 18 years) with moderate to severe active rheumatoid arthritis (RA) who have failed other anti-rheumatic drugs including Methotrexat (MTX) and patients with a severe, active and progressive rheumatoid arthritis (with or without prior MTX).

Patients who have been previously treated with other biologics (including TNF inhibitors) can be included in the NIS.

The inclusion and exclusion criteria adhere to the approved label as stated in the German Summary of Product Characteristics (SPC) “Fachinformation” for HUMIRA®. No additional inclusion and exclusion criteria are applicable since this project is non-interventional.

Patients to be included will be informed about the NIS and the use of their anonymous data. Patients willing to participate must provide their written informed consent to the investigator before entry into the NIS. The signed informed consent form will be added to the patient's file.

8.2 Number of Patients to be Enrolled

The NIS will include about 2500 patients in order to provide for the final evaluation of missed working days a sample size of $n = 850$ employed patients who are temporarily on sick leave during the study (see also Section 12.1 “Sample Size Calculation”).

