### **1.9 Sample size estimation**

*Sample size estimation for AGIL-CV as a supplement to AGIL:*

The sample size estimation is based on published data concerning the blood pressure of RA patients (14):

Assuming an alpha and beta error of 5% each, the following minimum number of RA patients is required at the evaluation time points of Months 12, 24 and 60:

- N=128 patients are required in order to detect a mean systolic blood pressure difference of 10 mmHg (given a mean systolic blood pressure of 128 mmHg with a standard deviation of 18 mmHg).
- N=136 patients are required in order to detect a mean diastolic blood pressure difference of 5 mmHg (given a mean diastolic blood pressure of 74 mmHg with a standard deviation of 11 mmHg).

In documentations with adalimumab, premature discontinuation has been observed for approx. 50% of patients in the course of a 60-month documentation duration. If this rate is taken into account; an overall number of N=300 patients is sufficient to address the primary research questions given the above-named estimations.

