12.1 Sample Size Calculation

The primary parameter of this documentation is work productivity, which is captured by the number of missed working days. The sample size calculation is based on the results of an interim analysis of a documentation of adalimumab in RA with 4640 patients, of whom 1417 patients had been employed part time or full time. The mean number of missed working days was 26 days (standard deviation of 55 days) during the last 12 month prior to adalimumab therapy. The correlation between baseline and follow-up report is estimated with $r = 0.5$. According to these numbers, 850 employed patients are required to detect a mean difference of 5 days within 12 months at the 0.05 significance level (two-sided) with a power of 0.80. Since 30 % of patients are employed, a total number of about 2500 employed and non-employed patients are required in order to detect the specified difference in missed working days.

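### Section 12.1 makes no allowance for stopping adalimumab, so 2500 enrolled patients cannot be said to provide 850 employed patients for the final evaluation of missed working days

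*Combined protocol and SAP*

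**What the plan says.** In the AGIL plan (combined protocol and SAP), Section 8.2 sets enrolment at about 2500 "in order to provide for the final evaluation of missed working days a sample size of" 850, meaning people in employment with temporary sick leave in the course of the study. Section 7 lists missed working days first among the primary target variables and puts the final analysis after 60 months of treatment.

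Section 12.1 states that "850 employed patients are required to detect a mean difference of 5 days within 12 months", using a two-sided 5% level and 80% power. It then moves to total enrolment in one step: "Since 30 % of patients are employed, a total number of about 2500 employed and non-employed patients are required". There is no step for patients who stop treatment.

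Section 8.4 says that a patient's documentation "ends either after 5 years or with the termination of the adalimumab therapy". Section 12.3 analyses observed cases, with an additional analysis restricted to patients complete at all visits.

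The AGIL-CV amendment (Protocol, Section 1.9) reports for adalimumab documentations that "premature discontinuation has been observed for approx. 50% of patients in the course of a 60-month documentation duration". It allows for this in its own sample: at most 136 patients are needed and 300 are planned.

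**The concern.** Section 8.2 describes the number available at the final evaluation, while Section 12.1 calculates only the number to enrol. The two agree only if nobody stops adalimumab, because stopping ends documentation and observed-case analysis does not replace the lost values. The sponsor's own amendment to the same study expects about half of patients to stop by Month 60 and enlarges the sub-study for that reason. The main plan has no corresponding term.

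Total enrolment is justified by this calculation. If the late comparison rests on about half the stated number, an inconclusive result would be read against 80% power that the design does not have.

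**Working it through.** **Inputs.** From Section 12.1: SD 55 days, r = 0.5, difference 5 days, two-sided 0.05, power 0.80, employed share 30%, total 2500. From AGIL-CV Section 1.9: 50% discontinuation by Month 60. Assumption: that rate applies equally to employed patients, and nobody leaves employment.

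**1. The plan's own figure.** SD of the within-patient change = 55 × √(2 × (1 − 0.5)) = 55 days.

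n = (55 × (1.960 + 0.842) / 5)² ≈ 950 (952 with the t distribution).

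So the stated inputs require about 950 patients, and 850 is not reproduced. At n = 850, power = Φ(5 × √850 / 55 − 1.960) = Φ(0.690) = 75.5%. For 850 to give exactly 80%, the SD of change would have to be 5 × √850 / 2.802 = 52.0 days (r about 0.55). Both SDs are carried below, so that the result does not depend on this discrepancy.

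**2. Enrolment step.** 2500 × 0.30 = 750, not 850. This gap exists before anyone stops treatment, so both starting numbers are shown.

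**3. Effect of discontinuation alone.** Power = Φ(5 × √n / SD − 1.960):

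| Employed patients with data | Power, SD 55 | Power, SD 52.0 |
|---|---|---|
| 850 (none stop) | 75.5% | 80% |
| 425 (50% stop) | 46.6% | 50.8% |
| 750 (none stop) | 70.2% | 74.9% |
| 375 (50% stop) | 42.1% | 46.1% |

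The noncentral t gives nearly the same: 46.4% at 425 and 41.9% at 375 with SD 55. In each pair discontinuation costs about 28 to 29 percentage points.

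**4. Detectable difference with 80% power.** 2.802 × SD / √n. At n = 425: 7.5 days (SD 55) or 7.1 days (SD 52.0). At n = 375: 8.0 or 7.5 days.

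**5. What the wording of 8.2 would require.** 850 / 0.50 / 0.30 ≈ 5667 enrolled. This shows the scale of the omission and is not a proposal.

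**6. If the sized comparison is at Month 12.** The documents give no 12-month discontinuation rate. Assuming, purely as a range, that 10% to 30% have stopped:

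- From 750: 675 to 525 remain, with power 66% to 55% (SD 55) or 70% to 60% (SD 52.0).
- From 850: 765 to 595 remain, with power 71% to 60% (SD 55) or 76% to 65% (SD 52.0).

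**7. Sub-study for comparison.** 136 / 0.50 = 272, which the planned 300 covers. The amendment makes the allowance that Section 12.1 omits.

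**The case against.** **Time point.** Section 8.2 does not name Month 60, and Section 12.1 sizes a difference within 12 months. A final report written after follow-up closes could present a 12-month contrast from the full cohort. This stands in part. Section 7 makes Month 60 the strong inference, but it is an inference. If Month 12 is meant, the 50% rate does not apply, but 8.2 and 12.1 still contain no allowance.

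**Recall period.** Mean 26, SD 55 and the 5-day difference are 12-month quantities, whereas Table 2 collects missed days over the last 6 months and visits are yearly after Month 12. A single Month 60 report is therefore a different measure, and r = 0.5 may not hold over five years. This stands, and the Month 60 power figures can only be labelled illustrations.

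**Source of the 50%.** It appears in the later amendment and describes adalimumab patients in general; nothing shows the rate among those employed. It is nevertheless the only rate in the documents.

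**Last visit.** A footnote to the physician schedule lets its final column be Month 60 or the last visit. Table 2, which holds missed working days, does not carry that footnote, and an early last visit would not be a 60-month value.

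**Stronger readings.** A reader might infer that discontinuation takes power from the stated 80% down to 42-46%. The documents do not support that. The fall from 850 to 375 includes the separate gap between 850 and 750, and setting 80% against 42% mixes two SDs, since 850 patients at SD 55 never give 80%. Nor do they support reading an explicit 80% power guarantee at Month 60.

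**Importance.** The objective is exploratory, the analysis mainly descriptive, and p-values are unadjusted. This stands and limits the severity, but it does not make the statement in 8.2 correct.

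**Conclusion.** The concern holds in this form: Section 12.1 has no discontinuation allowance, so the 850 employed patients that 8.2 assigns to the final evaluation are not provided by 2500 enrolments. At the 50% rate in the sponsor's amendment, the evaluable number at Month 60 is halved, and power for 5 days is roughly even odds or less (42% to 51%) whichever SD and starting number are used.

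This rests on three assumptions: the final evaluation is at Month 60, the 50% rate applies to employed patients, and the 12-month SD, effect and correlation carry over to a 6-month recall at Month 60. The third is doubtful, so the direction and the halving are firmer than the exact power. Two further problems are separate and are not caused by discontinuation: 30% of 2500 is 750, and the stated inputs need about 950 patients for 80% power.

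This should be fixed. It is not critical, because the analyses are exploratory.

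**What to change.** Keep the enrolment target. In Sections 8.2 and 12.1:

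- name the time point and recall period of the comparison for which the study is sized;
- state the expected number of employed patients with data at Months 12, 24 and 60 after discontinuation, with the rate used for each and its source;
- restate the power or detectable difference for those numbers, and label any Month 60 figure as resting on 12-month inputs;
- delete the statement that 2500 patients provide 850 for the final evaluation.

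The change is to wording only, with no extra patients or procedures. The cost is that the stated power becomes less favourable.

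### Sections 8.2 and 12.1 attach the same n = 850 to two different populations, and the one in 8.2 is selected on follow-up values of the outcome

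*Combined protocol and SAP*

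**What the plan says.** All references are to the combined protocol and SAP unless stated.

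- **Section 8.2** enrols about 2500 patients so that the final evaluation of missed working days has n = 850 "employed patients who are temporarily on sick leave during the study". It refers the reader to Section 12.1.
- **Section 12.1** names missed working days as the primary parameter and states that "850 employed patients are required to detect a mean difference of 5 days within 12 months"; alpha is 0.05 two-sided and power 80%. The inputs come from an earlier adalimumab documentation of 4640 patients, 1417 of them in part-time or full-time work. For the 12 months before therapy it reports: "The mean number of missed working days was 26 days"; the SD was 55 days, and the baseline/follow-up correlation is put at 0.5. The total of about 2500 is derived from a 30% employed share. No sick-leave condition appears.
- **Section 12.2** removes only patients previously treated with adalimumab from the efficacy analysis. **Section 12.3** analyses observed cases.
- **Section 7** lists missed working days first among the primary targets, as improvement against baseline.
- **Section 8.5.1, Table 2** collects missed working days, each time for the preceding 6 months, at month 0 and at months 6, 12, 24, 36, 48 and 60.

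**The concern.** The study is sized on this parameter, and the reader is given two descriptions of who counts towards the 850. Section 12 leaves the detail to a later SAP, whose author would find both.

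The 8.2 description is a problem in itself because sick leave during the study is a post-baseline value of the outcome. A patient with 40 missed days before therapy and none in any later report is the best result the study can show, yet would be outside the population. A patient with none before and 20 afterwards would be inside it. The mean and SD in 12.1 carry no such condition, so they cannot be assumed to describe that subset.

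**Working it through.** **1. The plan's own figure.** Inputs from 12.1: SD 55, r = 0.5, difference 5 days, two-sided alpha 0.05, power 0.80.

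- SD of the paired difference = 55 × √(2 × (1 − 0.5)) = 55.
- n = (55 × (1.960 + 0.842) / 5)², which is about 950. The stated 850 gives 75.5% power.

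So 850 is not reproduced by the paired formula. That is a separate matter on which this point does not depend. What matters here is that no sick-leave quantity enters the calculation.

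**2. The total.** 12.1 goes from employed patients to 2500 through the 30% employed share alone. 2500 × 0.30 = 750 employed patients, already below 850 (850 / 0.30 is about 2833). A sick-leave condition would lower the yield further. The share with sick leave is not given; at an assumed 50% it would be 750 × 0.5 = 375, and at 80% it would be 750 × 0.8 = 600. The plan has no step that allows for this, so its arithmetic belongs to the 12.1 population.

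**3. Size of the selection effect.** The documents give neither the share with sick leave nor the distribution of days, so this is an illustration. Assumptions: zero-inflated lognormal days with mean 26 and SD 55 before capping at 365; 30-70% of employed patients with sick leave at baseline; correlation about 0.5, equal between all windows; true change about -5 days in all employed patients. Negative means fewer missed days.

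Selection on sick leave in the same single follow-up window as the outcome:

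| Baseline share with sick leave | 30% | 40% | 50% | 60% | 70% |
|---|---|---|---|---|---|
| Benefit from fewer patients with any leave | +21 | +9 | +3 | 0 | -2 |
| Benefit from shorter leave only | +12 | +3 | -1 | -3 | -4 |

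Repeated runs put the top of this range at about +20 and the bottom at about -4.

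Selection on any sick leave over several follow-up windows, with change measured at the last:

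| Follow-up windows used for selection | Apparent change (days) |
|---|---|
| 2 | +1.4 to -5.0 |
| 3 | -2.5 to -5.6 |
| 5 | -5.1 to -6.3 |
| 6 | about -5 to -6 |

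The single-window bias weakens as the correlation rises. With benefit from fewer patients on leave and shares of 70, 50 and 40%, the apparent change is -1.8, +3.8 and +10.2 at a correlation near 0.5, but -3.3, +0.1 and +4.8 near 0.6.

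**4. Selecting on leave before baseline instead.** In the same model with no true change, patients with sick leave at baseline show an apparent fall of about 25, 8 and 2 days at shares of 30, 50 and 70%. This is regression to the mean, and a single-arm study has no control group to reveal it.

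**The case against.** Section 8.2 is an enrolment section, not a definition of the analysis population. It points to 12.1, and 12.1, 12.2, 12.3 and 7 contain no sick-leave restriction. The likeliest explanation is one loosely worded clause. Section 12.4 also calls the analyses exploratory. This stands: a reader might infer that the plan will certainly analyse only patients with sick leave, and the documents do not support that.

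A reader might also infer that following 8.2 would always hide or reverse a true improvement. That does not hold either. The clause refers to the study, which lasts up to 60 months with six follow-up reports. A patient is lost only if none of those reports shows sick leave. For patients followed to the end, the bias in the illustration is about nil or slightly favourable.

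The objection does not remove the contradiction. 8.2 ties its clause explicitly to the final evaluation of missed working days, and nothing says which section governs. Nor will every patient have six reports: under Section 8.4 documentation ends when adalimumab stops, and Section 1.9 of the AGIL-CV amendment cites about 50% premature discontinuation over 60 months. How many patients would have only one or two reports is not given.

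**Conclusion.** The inconsistency is real: one n, two populations. The supporting arithmetic and the population section agree with 12.1, so 8.2 is the text out of line, possibly through wording alone.

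Taken literally, 8.2 would condition on the outcome. The consequence for a true change of about -5 days ranges from an apparent +20 to -4 days (same single window) to about -5 to -6 (any of six reports), under the assumed distribution, a 30-70% sick-leave share and a correlation of about 0.5. The bias is material mainly for patients with one or two follow-up reports. No single figure can be given, because the documents fix neither the window nor the share.

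**What to change.** In Section 8.2, delete the relative clause about sick leave so that the 850 are simply employed patients, as in 12.1. In the SAP, state that change in missed working days is evaluated in all patients employed at baseline, with a reported zero counted as zero and a missing report left missing, in line with 12.3.

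Do not substitute a before/after analysis in patients chosen for sick leave before baseline. If such a subgroup is shown, label it descriptive and subject to regression to the mean.

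The cost is one clause in 8.2 and one sentence in the SAP. Table 2 already collects professional status and missed working days at month 0, so no new data are needed.
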